Table 2: Dosing Scheme for Aducanumab by Treatment Group and ApoE ε4 Carrier Status: Long-Term Extension Period

Doses (every 4 weeks)		1	2	3	4	5	6	7- EOS	
LTE Treatment Group	LTE Treatment Group Stratified by ApoE Status ¹	Dose (mg/kg)							
Early Start High	Early Start High Dose – ApoE ε4 (+)	10							
Dose	Early Start High Dose – ApoE ε4 (-)	10							
Early Start Low	Early Start Low Dose – ApoE ε4 (+)	3							
Dose	Early Start Low Dose – ApoE ε4 (-)	6							
Late Start High	Late Start High Dose – ApoE ε4 (+)	1	1	3	3	6	6	10	
Dose	Late Start High Dose – ApoE ε4 (-)	1	1	3	3	6	6	10	
Late Start Low	Late Start Low Dose – ApoE ε4 (+)	1 1 3							
Dose	Late Start Low Dose – ApoE ε4 (-)	1	1	3	3	3	3	6	

¹ ApoE ε4 status recorded in the Interactive Voice/Web Response System (IXRS).

[figure not shown]
Individual dose adjustments may be implemented in subjects who develop amyloid related imaging abnormalities (ARIA). See Protocol Section 7.2.1.

The total duration of study participation for each subject only participating in the placebo-controlled period of the study will be up to approximately 102 weeks, including a series of screening visits within 8 weeks before administration of the first dose, a 76-week placebo-controlled treatment period, and a safety follow-up (FU) period of approximately 18 weeks after the final dose. The total duration of study participation for each subject participating in the placebo-controlled period and the LTE period will vary and be up to approximately 362 weeks, including a series of Screening visits within 8 weeks before administration of the first dose, a 76-week placebo-controlled treatment period, a 4-week FU period, a 256-week aducanumab dose-blind treatment period, and a safety FU period of approximately 18 weeks after the final dose.

Investigators, study site staff (except for the designated unblinded pharmacist/technician), and study subjects will be blinded to the subjects' randomized treatment assignment for the placebo-controlled period. During the LTE period, investigators and subjects will remain blinded to the treatment assignment in the placebo-controlled period and the aducanumab dose for the LTE period.

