3.5.2.1 Summary and incidence analysis

Overall summary of AE table will be done for the LTE period, as well as for the placebo-controlled and LTE active treatment period presented by LTE treatment group as well as LTE treatment group stratified by ApoE status. The following information will be summarized: the number of subjects with any AE, with any AE by maximum severity, the number of subjects with any related AE (related to study drug as assessed by investigator), the number of subjects with SAE, the number of subjects with related SAE, the number of subjects with AE leading to study drug discontinuation, the number of subjects with AE leading to study withdrawal, and the number of deaths.

The sorting order of AE incidence tables, unless otherwise specified, will be by decreasing frequency order of "BIIB037 total" column within each category in the tables presented by LTE treatment group, and by decreasing frequency order of "BIIB037 early start total" column within each category in the tables presented by LTE treatment group stratified by ApoE status. A subject is counted only once within each category in each table. For example, for the table of AEs by system organ class and preferred terms sorted by decreasing frequency presented by LTE treatment group, system organ class will be presented in decreasing frequency order of BIIB037 total column, and within each system organ class, preferred terms will be presented in decreasing frequency order of BIIB037 total column. A subject is counted only once within each system organ class and preferred term.

The following AE incidence tables will be provided for the LTE period (presented both by LTE treatment group and by LTE treatment group stratified by ApoE status, unless otherwise specified):

- 1. AEs by system organ class and preferred term sorted by decreasing frequency
- 2. AEs by system organ class and preferred term sorted by alphabetical order analysis (by LTE treatment group)
- 3. AEs by system organ class, high level group term and preferred term (by LTE treatment group)
- 4. AEs by system organ class (by LTE treatment group)
- 5. AEs by preferred term
- 6. AEs with an incidence of 5% or more in any treatment group by preferred term
- 7. Severe AEs by system organ class and preferred term
- 8. Severe AEs by preferred term (by LTE treatment group)

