- 9. AEs by maximum severity by system organ class and preferred term (by LTE treatment group) (System organ class will be presented alphabetically. Preferred terms will be presented in decreasing frequency order. Maximum severity will be presented within each preferred term in the order of mild, moderate, severe, unknown and total.

Final V1.0

A subject will be counted only once at the maximum severity within each system organ class and preferred term.)

- 10. AEs by maximum severity by preferred term (by LTE treatment group) (Preferred terms will be presented in decreasing frequency order. Maximum severity will be presented within each preferred term in the order of mild, moderate, severe, unknown and total. A subject will be counted only once at the maximum severity within each preferred term.)
- 11. Related AEs by system organ class and preferred term
- 12. SAEs by system organ class and preferred term
- 13. SAEs by preferred term
- 14. Related SAEs by system organ class and preferred term
- 15. AEs that led to discontinuation of study treatment by system organ class and preferred term
- 16. AEs that led to withdrawal from study by system organ class and preferred term
- 17. SAEs with fatal outcome by system organ class and preferred term
- 18. AEs that occurred within 2 hours from infusion start by system organ class and preferred term (by LTE treatment group)

The following listings will be provided for the placebo-controlled and LTE period:

- 1. Listing of AEs
- 2. Listing of SAEs
- 3. Listing of AEs that led to discontinuation of study treatment
- 4. Listing of AEs that led to withdrawal from study
- 5. Listing of AEs that occurred within 2 hours from infusion start
- 6. Listing of AEs related to PET ligands
- 7. Listing of SAEs with fatal outcome
- 8. Listing of AEs for subjects with treatment-emergent positive anti-BIIB037 antibody

3.5.2.2 Incidence and incidence rate analysis for placebo-controlled and LTE active treatment period

Due to the different length of placebo-controlled and LTE active treatment period in early start versus late start subjects, both incidence tables and follow-up adjusted incidence rate tables will be used for AE analyses in this period. The entire follow-up time is from the first dose in active treatment period (first dose in placebo-controlled period for early start subjects and first dose in LTE period for late start subjects) until the last day in the study.

Final V1.0

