3.5.3.2 Incidence and summary of ARIA

Incidence of ARIA-E, ARIA-H, ARIA-E and ARIA-H (not necessarily concurrent), concurrent ARIA-E and ARIA-H, ARIA-E or ARIA-H, isolated ARIA-H (only ARIA-H, no ARIA-E), ARIA-H microhemorrhage, ARIA-H macrohemorrhage and ARIA-H superficial siderosis in the LTE period and in the placebo-controlled and LTE active treatment period will be summarized based on both AE eCRF and MRI data. If there is any discrepancy in incidence between the two data sources, a listing of the subjects and ARIA events with discrepancy will be provided. In addition, the incidence table based on AE eCRF source will also be done by LTE treatment group (analysis display A in Appendix 4.1).

Number of subjects with each type of ARIA, maximum severity and worst symptomatic status of the type of ARIA being analyzed in the LTE period and in the placebo-controlled and LTE active treatment period will be summarized based on AE eCRF. For subjects with symptomatic ARIA, the maximum severity of symptoms will also be summarized.

Summary of concurrent ARIA-E and ARIA-H will be provided including the following information for the LTE period and for the placebo-controlled and LTE active treatment period: number of subjects with concurrent ARIA-E and ARIA-H (and further broken down to each type of ARIA-H), the severity of ARIA-E based on MRI, the symptomatic status of ARIA-E, the severity of symptoms based on AE eCRF. For subjects with recurrent ARIA-E

Final V1.0

events, if there is an event concurrent with ARIA-H, it will be used for the summary, and the first concurrent event will be used if there are more than one event concurrent with ARIA-H.

An incidence table of AEs considered by the investigator to be related to ARIA by system organ class and preferred term for subjects with symptomatic ARIA in the placebo-controlled and LTE active treatment period will be provided, as well as a listing of these AEs. Similarly, an incidence table of AEs related to ARIA for subjects with symptomatic ARIA and severe symptoms will be provided, as well as a listing of these AEs.

Listings of AE records for each type of ARIA events and listings of MRI assessments for subjects with each type of ARIA events will be provided.

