Please refer to the placebo-controlled SAP for the parameters and criteria for potentially clinically significant laboratory abnormalities analyses.

The number of subjects with potentially clinically significant laboratory abnormalities post-baseline will be summarized for the placebo-controlled and LTE active treatment period.

Subjects need to have at least one post-baseline evaluation in the active treatment period and a baseline value not potentially clinically significant (including missing) in order to be included in the analysis.

Same as the shift analysis, for early start subjects, the placebo-controlled baseline will be used and abnormalities that occurred in either placebo-controlled or LTE period will be included. For late start subjects, the LTE baseline will be used and PCS abnormalities that occurred in the LTE period based on LTE baseline will be included.

Potential serious hepatotoxicity

In this SAP, we define potential serious hepatotoxicity as ALT or AST > 3x ULN and total bilirubin > 2x ULN at any time post-baseline in the placebo-controlled and LTE active CONFIDENTIAL

Final V1.0

treatment period (not necessarily concurrent). A scatterplot of the maximum post-baseline ALT or AST value relative to ULN and maximum post-baseline total bilirubin value relative to ULN (not necessarily concurrent) for each subject will be provided. A line plot of ALT, AST, ALK and total bilirubin values over time in the active treatment period for subjects with potential serious hepatotoxicity will be provided. In addition, subjects with ALT > 1x ULN, >3x ULN, >5x ULN, >5x ULN, >10x ULN or >20x ULN, subjects with AST > 1x ULN, >3x ULN, >5x ULN, >10x ULN or >20x ULN, subjects with total bilirubin >1x ULN or >2x ULN, subjects with ALP >1x ULN or >1.5x ULN, and subjects with AST or ALT > 3x ULN post-baseline accompanied by concurrently elevated total bilirubin >1.5x ULN or > 2x ULN in the active treatment period will be presented. Concurrent is defined as on the same day. A listing of subjects with potential serious hepatotoxicity will be provided.

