3.5.5 C-SSRS Data

The Columbia Suicide Severity Rating Scale (C-SSRS) is an assessment that evaluates suicidal ideation and behavior. There are 5 "Yes/No" questions on suicidal ideation following the increasing severity order: (1) Wish to be dead, (2) Non-specific active suicidal thoughts, (3) Active suicidal ideation with any methods (not plan) without intent to act, (4) Active suicidal ideation with some intent to act, without specific plan, (5) Active suicidal ideation with specific plan and intent, and 6 "Yes/No" questions on suicidal behavior following the increasing severity order: (6) Preparatory acts or behavior, (7) Aborted attempt, (8) Interrupted attempt, (9) Actual attempt, (10) Suicidal behavior, (11) Suicide (only at post-baseline visits). Another "Yes/No" question of whether the subject has engaged in non-suicidal self-injurious behavior is also collected.

The summary table for C-SSRS will be conducted for the placebo-controlled and LTE active treatment period. Number of subjects who answered "Yes" to each of the 11 questions post-baseline, subjects who answered "Yes" to at least one question for suicidal ideation, subjects who answered "Yes" to at least one question for suicidal behavior, and subjects who have engaged in non-suicidal self-injurious behavior will be presented. A listing of subjects with any suicidal ideation or behavior at baseline or post-baseline will be provided for placebo-controlled and LTE period.

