3.5.7 Vital Sign Data

Vital sign parameters include body temperature, systolic blood pressure, diastolic blood pressure, heart rate, respiration rate and weight. Vital signs will be measured with the subject CONFIDENTIAL

Final V1.0

supine and after the subject has been resting for at least 10 minutes. The descriptive statistics for actual values will be summarized at each visit in the placebo-controlled and LTE period. Plot of mean vital sign values in the placebo-controlled and LTE period will be provided.

Summary of change from baseline including number of evaluable subjects, mean, standard deviation, median, 25% and 75% quartiles, minimum, and maximum values will be summarized at each visit in the placebo-controlled and LTE active treatment period. Placebo-controlled baseline will be used for early start subjects and LTE baseline will be used for late start analysis.

The analysis of vital signs will also focus on the incidence of clinically relevant outliers. Please refer to the placebo-controlled SAP for the criteria to assess potential clinically relevant outliers in vital sign. The incidence and percentage of clinically relevant outliers determined by each criterion will be summarized in the placebo-controlled and LTE active treatment period. A listing of subjects with clinically relevant vital signs in the placebo-controlled and LTE active treatment period will also be provided.

Visit windows for by visit summaries

For vital sign by visit summaries, the analysis visit should be defined using windows (see Table 6 below). For the same parameter for a subject, if there is more than 1 record in the same analysis visit window, then select the record closest to the target visit day. If there are 2 records in the same analysis visit window with the same distance from the target visit day, then select the record with the later date.

Table 6: Visit Windows for Vital Sign by Visit Summaries

	Analysis visit window ¹			
Analysis visit	For subjects who received the	For subjects who received the		
	first dose of aducanumab in	first dose of aducanumab in		
	the placebo-controlled period	the LTE period		
Baseline	Last value prior to the first dose of	Last value prior to the first dose of		
	aducanumab	aducanumab		
Week 4	[2, 42]	[2, 42]		
Week 8	[43, 70]	[43, 70]		
Week x	$[7x -13, 7x+14]$ for $8 \le x \le 72$	$[7x -13, 7x+14]$ for $8 \le x \le 252$		
Week 76	[519, the end day of the placebo- controlled period ¹]	$[7x -13, 7x+14]$ for $8 \le x \le 252$		

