3.7.2 Immunogenicity analysis

Immunogenicity population will be used to analyze immunogenicity data. LTE safety treatment groups will be used for immunogenicity analysis. Tables will be presented by LTE treatment group (late start low dose, late start high dose, early start low dose, early start high dose, and in addition late start total, early start total and BIIB037 total; analysis display A in Appendix 4.1). Listings will be presented by treatment group stratified by ApoE status.

A summary table of subjects with treatment-emergent positive anti-aducanumab antibody responses in the placebo-controlled and LTE active treatment period will be provided. The number and percentage of anti-aducanumab positive results will be summarized at each visit as well as at any time post-baseline in this period. Subjects with persistent response and

Final V1.0

subjects with transient response in this period will be presented. A listing of immunogenicity data in placebo-controlled and LTE period for subjects with anti-aducanumab antibody positive results will also be provided.

Visit windows for by visit summaries

For immunogenicity by visit summaries, the analysis visit should be defined using visit windows (see Table 7 below). If there is more than 1 value in the same analysis visit window for a subject, then the closest record to the target visit day will be used for the by visit analysis. If there are 2 values in the same analysis visit window with the same distance from the target visit day for a certain parameter for a subject, then the record with the later date will be used for the by visit analysis. If there are 2 values on the same day for a certain parameter for a subject, then the record with the later time will be used for the by visit analysis.

Table 7: Visit Windows for Immunogenicity by Visit Summaries

	Analysis visit window ¹			
	For subjects who received the	For subjects who received the		
	first dose of aducanumab in	first dose of aducanumab in		
Analysis visit	the placebo-controlled period	the LTE period		
Baseline	Last value prior to the first dose of	Last value prior to the first dose of		
	aducanumab	aducanumab		
Week 24	[2, 196]	[2, 252]		
Week 32	[197, 308]	NA		
Week 56	[309, 470]	[253, 420]		
Week 78	[471, end day of the placebo-	[421, 609]		
	controlled period ²]			
Week 80	[start day of the LTE period ³ , 644]	NA		
Week 104	[645, 812]	[610, 1260]		
Week 128	[813, 980]	NA		
Week 152	[981, 1169]	NA		
Week 182	[1170, 1820]	≥ 1261		

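### The LTE SAP adjusts for unequal follow-up in nine AE tables and ARIA-E, but leaves deaths, discontinuations and other ever-occurred safety counts over the same period unadjusted

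*SAP*

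**What the plan says.** All references are to the LTE part of the SAP unless stated.

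- Section 3.1.2 defines an active treatment period across both study periods. Early-start subjects bring all their data; late-start subjects bring LTE data only. Anyone dosed in the period is included, so the early-start columns also hold subjects who never enter the LTE.
- Section 3.5.2.2 gives its reason for adding rates: "Due to the different length of placebo-controlled and LTE active treatment period in early start versus late start subjects". It then lists nine tables that receive a follow-up adjusted rate: all AEs (three tables), severe AEs (two), related AEs, SAEs (two) and related SAEs.
- ARIA-E gets a follow-up adjusted rate (3.5.3.3), an exposure-adjusted rate (3.5.3.4) and a Kaplan-Meier plot (3.5.3.5).
- Deaths, AEs leading to discontinuation and AEs leading to withdrawal appear over this period only as counts in the overall table of 3.5.2.1: "Overall summary of AE table will be done for the LTE period, as well as for the placebo-controlled and LTE active treatment period".
- Laboratory shifts, worst grade, potentially clinically significant (PCS) values and potential hepatotoxicity (3.5.4.2) are counts of subjects. For PCS values: "The number of subjects with potentially clinically significant laboratory abnormalities post-baseline will be summarized for the placebo-controlled and LTE active treatment period".
- C-SSRS (3.5.5): "The summary table for C-SSRS will be conducted for the placebo-controlled and LTE active treatment period". ECG shifts (3.5.6) are handled in the same way. Vital-sign outliers (3.5.7) are those "determined by each criterion will be summarized in the placebo-controlled and LTE active treatment period".
- Antibody positivity (3.7.2) "will be summarized at each visit as well as at any time post-baseline in this period", with persistent and transient status counted as well.

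**The concern.** The plan identifies unequal observation time as a problem and corrects it for some outcomes but not for others measured over the same period. Each uncorrected item counts subjects who ever had an event. Such a count grows with time observed and with number of samples, even when the underlying risk is the same. Section 3.5.4.2 uses every value, not one per visit window, so extra sampling feeds straight into the laboratory counts. Section 3.5.2 counts deaths and AEs leading to withdrawal however long after the last dose they occur.

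The safety displays set late-start and early-start columns side by side. A reader could take a difference due to observation time as cumulative toxicity, or miss a real difference that unequal follow-up hides. Long-term safety and tolerability is the first-listed LTE objective.

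**Working it through.** **1. Planned durations (section 2.1).** The SAP gives "a 76-week placebo-controlled treatment period, a 4-week FU period, a 256-week aducanumab dose-blind treatment period, and a safety FU period of approximately 18 weeks", after up to 8 weeks of screening.
- Check of the stated total: 8 + 76 + 4 + 256 + 18 = 362 weeks, as the SAP says.
- Active-period follow-up, early-start LTE entrant: 76 + 4 + 256 + 18 = 354 weeks.
- Late-start: 256 + 18 = 274 weeks.
- Difference: 80 weeks; ratio 354/274 = 1.29.

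**2. Scheduled windows after baseline (Tables 5 and 7).**
- Laboratory, early: Weeks 24, 48, 72, 78, 104, 128, 152, 176, 232, 284, 336 = 11. Late: Weeks 24, 48, 72, 104, 152, 232, 284 = 7.
- Antibody, early: Weeks 24, 32, 56, 78, 80, 104, 128, 152, 182, 338 = 10. Late: Weeks 24, 56, 78, 104, 182 = 5.

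**3. Effect of visit count alone.** Assume the same probability p at each visit and independent visits; the chance of ever being positive is 1 − (1 − p)^k.
- Laboratory, p = 1%: 1 − 0.99^11 = 10.5% against 1 − 0.99^7 = 6.8%.
- Laboratory, p = 2%: 19.9% against 13.2%.
- Antibody, p = 1%: 1 − 0.99^10 = 9.6% against 1 − 0.99^5 = 4.9%.

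Persistence within a subject would shrink these gaps, so they lean towards the upper end.

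**4. Effect of follow-up time.** Assume the same constant hazard, 5 per 100 person-years, in both groups. The crude proportion is 1 − exp(−0.05 × T/52.18), with T in weeks. L is the LTE follow-up at the data cutoff. First let every early-start subject enter the LTE (T = 80 + L against L). Then let 70% enter, with non-entrants followed for 40 or 94 weeks (76 + 18 = 94). The 70% borrows the 30% drop-out assumption of the placebo-controlled SAP, section 3, for range only.

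| L (weeks) | Late | Early, all enter | Ratio | Early, 70% enter, 40 wk | Ratio | Early, 70% enter, 94 wk | Ratio |
|---|---|---|---|---|---|---|---|
| 52 | 4.9% | 11.9% | 2.44 | 9.4% | 1.94 | 10.9% | 2.24 |
| 104 | 9.5% | 16.2% | 1.70 | 12.4% | 1.31 | 13.9% | 1.47 |
| 274 | 23.1% | 28.8% | 1.25 | 21.3% | 0.92 | 22.7% | 0.98 |

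The mean follow-up gap is f(80 + L) + (1 − f)m − L, where f is the fraction entering and m the non-entrants' follow-up. It is +80 weeks when all enter. At f = 0.7, m = 40, L = 274 it is 0.7 × 354 + 0.3 × 40 − 274 = −14 weeks.

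**5. Which rate removes this.** With all subjects entering, hazards of 0.5 to 20 per 100 person-years and L from 26 to 274 weeks, the crude ratio runs from 4.06 to 1.14. The follow-up adjusted rate (definition 1 in the SAP's incidence definitions) divides by entire follow-up and gives 1.00 to 0.86, so it over-corrects frequent first events. The exposure-adjusted rate (definition 2) stops the clock at the first event and gives 1.00.

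**6. Where a rate is not enough.** Visits per week differ. Laboratory: 11/336 against 7/256, ratio 1.20. Antibody: 10/338 against 5/258, ratio 1.53. (The late-start spans are 336 − 80 and 338 − 80 weeks.) Outcomes detected only at visits need matched visits as well as matched time.

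**The case against.** Several stronger readings are tempting, and the document does not support them.

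- A reader might infer that ARIA-H is shown only as crude incidence. Its own tables in 3.5.3.2 are incidence tables, covering findings up to "ARIA-H superficial siderosis in the LTE period and in the placebo-controlled and LTE active treatment period will be summarized". But ARIA-H is recorded on the AE form and coded to preferred terms (placebo-controlled SAP, Table 6), so it enters the follow-up adjusted tables in 3.5.2.2, items 1 and 3. What remains is small: micro- and macrohemorrhage share one preferred term, and ARIA-H has no exposure-adjusted rate or Kaplan-Meier plot.
- A reader might infer that all laboratory, vital-sign and antibody results are unadjusted. Numeric changes and antibody positivity are also given by visit, in windows counted from the first aducanumab dose. Those summaries do not correct the threshold, shift, worst-grade or any-time counts.
- A reader might infer a biased planned comparison. Early-against-late comparisons are named only for efficacy (3.3.1) and amyloid PET (3.4.4). Safety is descriptive.
- A reader might infer that early-start subjects are always seen 80 weeks longer and so always look worse. That gap applies to LTE entrants only; step 4 shows that it can vanish or reverse.

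It is also fair that discontinuations, withdrawals and fatal SAEs have full tables for the LTE period alone, where planned follow-up is equal, and that fatal SAEs count within the adjusted SAE tables. Neither gives a time-adjusted figure for these categories over the combined period.

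**Conclusion.** The point holds in this limited form. Section 3.5.2.2 accepts that unequal length calls for rates, yet over the same period no time-adjusted summary is planned for deaths, AE discontinuations or AE withdrawals as categories. The same is true of laboratory shift, grade, PCS and hepatotoxicity counts, ECG shifts, C-SSRS, vital-sign outliers, and any-time, persistent or transient antibody status.

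The 80-week gap for LTE entrants and the 11 v 7 and 10 v 5 window counts come directly from the SAP. The percentages rest on assumed equal risks, LTE entry and cutoff. At 5 per 100 person-years, the crude ratio ranges from 2.44 to 0.92 with no true difference. Because even the direction is uncertain, the crude columns cannot be compared with each other. Efficacy conclusions are unaffected.

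**What to change.** 1. Add fatal SAEs, AEs leading to discontinuation and AEs leading to withdrawal to the list in 3.5.2.2. Report them with the exposure-adjusted incidence rate the SAP already defines (definition 2), starting at the first dose of the active treatment period.
2. For the laboratory counts, vital-sign outliers, ECG shifts, C-SSRS and any-time antibody positivity, add a version cut at the same time since first active dose in all groups and limited to visits scheduled for both. Define those visits by day ranges, because the same label can cover different days: in Table 5, Week 284 is days 1807–2170 for early start and day 1709 onwards for late start.
3. In the tables left as they are, show total follow-up time and number of assessments per column.
4. Optionally, give the ARIA-H subtypes the exposure-adjusted rate already used for ARIA-E.

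The cost is SAP wording and a few extra tables or columns; no new data are needed. Later early-start data drop out of the equal-time display but remain in the full-period tables and the listings.
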